8.4 SAMPLE SIZE CALCULATION

The sample size is calculated to achieve 80% power for the futility analysis described above using a one-sided alpha level of 0.10. It is anticipated that approximately 28% of control subjects will have mRS 0-2 at 3 months; this is based on the weighted average of the good outcome proportions reported in the placebo-treated subjects of the Factor VII, FAST, GAIN, and CHANT trials [Haley 2005; Lyden 2007; Mayer 2005-2008]. If the true good outcome proportions in the DFO and placebo arms are identical ($\pi_{tx}=0.28$, $\pi_{ctrl}=0.28$, a truly futile situation), 254 subjects (127 in each arm) are required to test the futility hypothesis with 80% power. This calculation takes into account the 0.12 null value specified in the futility hypothesis [Chow, 2003]. The primary analysis will be conducted according to a modified Intent-to-Treat (ITT) principle, wherein subjects in whom the study drug infusion is not initiated will be excluded from the analysis. Therefore, the final sample size was inflated by a factor of 1.11 (Friedman, Furberg, and DeMets) to account for dilution of the treatment effect associated with a conservative drop-out rate of 5% (due to loss-to-follow-up (LTFU) and

withdrawal of consent), and an additional factor of 1.04 to account for randomized subjects in whom the study drug is not initiated. Therefore, the final sample size is 294 subjects.

8.5 LOSS-TO-FOLLOW-UP AND MISSING DATA

Extensive efforts will be made to keep missing data, particularly the primary outcome (mRS at 90 days), to a minimum, and to ensure near complete follow-up. Missing primary outcome data will be imputed via standard multiple imputation (MI) methods (i.e. via logistic regression model predicting outcome based on pertinent baseline and treatment data). As a sensitivity assessment, we will use the Last Observation Carried Forward (LOCF) approach, wherein the last available score will be carried forward for missing day 90 assessments. If the treatment effect is robust, we expect to reach similar conclusions via these imputation methods, particularly for minimal missing data (<5%).

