3.2 OVERVIEW OF STUDY DESIGN

This is a prospective, multi-center, double-blinded, randomized, placebo-controlled, phase-II clinical trial. The total sample size required is 294 subjects with ICH. Subjects will be randomized in a 1:1 ratio to receive either DFO at 32 mg/kg/day (up to a maximum daily dose of 6000 mg/day), or a matching saline vehicle (placebo), given by IV infusion for 3 consecutive days, in a blinded manner. Treatment will be initiated within 24 hours after ICH symptom onset. Subjects will undergo repeated clinical, imaging, and laboratory evaluations at regular intervals throughout their participation in the study, from the day of randomization until day 180. All adverse events will be assessed until day-7 or discharge (whichever is earlier), and new SAEs until day-90. Mortality and continuing SAEs will be assessed until day 180. Functional status will be determined by mRS scores, in person at 30 ± 7 and 90 ± 7 days; the patients or their surrogates will be contacted by phone on days 60 ± 7 and 180 ± 7 to assess mRS [Merino, 2005].

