Subjects who receive the study drug(s) will be evaluated daily for the first 3 days (during study drug infusion while in hospital) and on day-7 or discharge from the hospital, whichever occurs first. Clinic visits will take place on days 30 ± 7 and 90 ± 7 . Telephone interviews will be conducted on day 60 ± 7 and 180 ± 7 .

The following assessments should be performed **after each daily infusion** (every 24 ± 6 h) and through the day following completion of the last infusion: 1) General physical examination; 2) Visual and auditory assessments; 3) Neurological examination, including NIHSS and GCS; and 4) Vital signs, including blood pressure and heart rate. A repeat head CT scan and blood samples for hematology, serum chemistry, renal and hepatic function tests, coagulation studies, and urine analysis should be obtained within 24 ± 6 h following the last infusion of the study drug. Vital signs (blood pressure and pulse) and neurological functions should be assessed at least once every 4h during intravenous drug infusions. Daily urinary output checks should be carried out every day until the day following the last infusion. In addition, the following data must be checked at least once daily for all intubated patients (or more frequently in patients with changes in respiratory status requiring changes in ventilator settings and increased oxygen requirement) throughout day-7 or discharge and entered into Web-DCU™: 1) $\text{PaO}_2/\text{FiO}_2$ ratio; 2) Plateau and peak pressures; and 3) Chest X-ray results (when available). **A chest x-ray is required if the $\text{PaO}_2/\text{FiO}_2$ ratio is < 300 .**

On day-7 or Discharge (whichever comes first), the following assessments are done: mRS, NIHSS, GCS, MoCA and visual and auditory assessments.

During hospitalization, the NIHSS and GCS should be done any time a subject's neurological status deteriorates, or whenever the investigator believes it is prudent to do an assessment. Laboratory assessments beyond those required for the study should be done whenever clinically indicated.

The **Day-30 (± 7)** will be an in-person visit comprised of a general physical examination, visual and auditory assessments, review of SAEs, and assessments of NIHSS, SIS-16, MoCA and mRS.

The **Day-60 (± 7)** assessments, which will be completed via telephone, will be comprised of a functional assessment to obtain a score on mRS and query for SAEs.

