The **Day-90 (± 7)** visit will be an in-person visit comprised of a general physical examination, visual and auditory assessments, and assessments of NIHSS, MoCA, SIS-16, and mRS. However, a telephone interview to obtain a score on mRS (the primary outcome measure) may be allowed on a case-by-case basis, after consultation with the PI, if the subject is unable to return for an in-person evaluation.

The **Day-180 (± 7)** assessments, which will be completed via telephone, will be comprised of a functional assessment to obtain a score on mRS.

A study staff member certified in NIHSS and mRS and experienced in administering GCS, SIS-16, and MoCA should perform the assessments at all time points. We require that all assessments at all time points be performed by the same blinded

investigator, whenever possible, to minimize inter-rater variability. Data on the subject’s functional status (mRS and SIS-16) can be obtained from a proxy if the subject is unable to provide the information. Please refer to Appendix V for details of NIHSS, GCS, SIS-16, and MoCA scales.

Concomitant medications and non-drug therapies should be assessed at all points of contact with the subject after study drug initiation. All adverse events (serious and non-serious) should be assessed until day-7 or discharge, whichever occurs first. All new SAEs will be monitored until day-90, resolution of the SAE, or withdrawal of consent, whichever is earlier. Continuing SAEs beyond day-90 will be monitored until day-180.

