8.3 STUDY SAMPLES

ALL analyses will involve data from two samples:

1- Modified Intent-to-Treat (mITT): Outcome data from all subjects who are randomized and in whom the study infusion begins, even if it is discontinued prematurely, will be analyzed. Classically, ITT analysis is used in Phase III trials and includes all subjects randomized, regardless of whether they receive the treatment or not. However, in order to evaluate the efficacy of DFO as administered, randomized subjects in whom the study infusion is never initiated will be excluded from the primary analysis. As a sensitivity analysis, the futility hypothesis will also be assessed according to the ITT principle. All subjects randomized will be included and considered in the treatment group to which he/she was randomized, regardless of the treatment actually received. The outcomes for subjects in whom treatment is never initiated will be imputed based on available baseline data.

Safety analysis will involve data from all patients in whom study infusion begins, even if it is discontinued prematurely (i.e. the mITT sample).

2- Per-protocol sample, i.e. all subjects who have at least one post-treatment assessment and no major protocol violations that affect the analysis. The Executive Committee (EC) will adjudicate major protocol violations and patients' inclusion in the per-protocol population before unblinding. Analyses based on the per-protocol sample will be supportive in nature.

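### The primary imputation of missing day-90 mRS uses baseline and treatment data only; the follow-up mRS scores already collected should be added to it

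*Protocol*

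**What the plan says.** Section 8.5 imputes missing primary outcomes by multiple imputation "via logistic regression model predicting outcome based on pertinent baseline and treatment data". The clause is introduced by *i.e.*, so it defines the model and does not merely illustrate it. Treatment data most naturally means assigned arm or exposure. As a sensitivity analysis, "the last available score will be carried forward for missing day 90 assessments".

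For the intention-to-treat sensitivity analysis, section 8.3 states: "The outcomes for subjects in whom treatment is never initiated will be imputed based on available baseline data". Those subjects have nothing else.

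Treated subjects have more:

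- **Day 7 or discharge** (section 6.1.1): "the following assessments are done: mRS, NIHSS, GCS, MoCA and visual and auditory assessments".
- **Day 30** (section 6.1.1): an in-person visit that includes mRS.
- **Day 60** (section 6.1.1): a telephone contact "comprised of a functional assessment to obtain a score on mRS and query for SAEs".
- **Day 180**: section 3.2 says "the patients or their surrogates will be contacted by phone on days 60 ± 7 and 180 ± 7 to assess mRS".

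No section brings these scores into the primary imputation. At day 90 itself, "a telephone interview to obtain a score on mRS (the primary outcome measure) may be allowed on a case-by-case basis". Section 8.4 allows for "a conservative drop-out rate of 5"%, covering loss to follow-up and withdrawal of consent, and section 8.5 speaks of less than 5% missing.

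**The concern.** A subject lost before day 90 can have up to three earlier scores on the endpoint's own scale, and these are likely to be the best available predictors of the missing value. Leaving them out means assuming that, within arm and baseline profile, a subject last seen at mRS 1 and one last seen at mRS 5 were equally likely to be lost. If that fails differently in the two arms, the imputed risk difference is biased.

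Two errors are possible. A useful drug may be declared futile too often, which is the error the one-sided 0.10 level is meant to control. Or a useless drug may be stopped too rarely. LOCF would use the interim scores, but the go/no-go decision rests on the primary test. The two methods also differ in both data and assumption, so a disagreement between them could not be traced to either one.

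The sponsor's own Phase I series (section 2.2.2) shows the situation arising. Two of 20 subjects withdrew before day 90, one last scored at mRS 5 and one at mRS 1. The section 8.5 model would ignore both scores. With one loss on each side of the 0–2 cut in a single-arm study, this says nothing about a difference between arms.

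A smaller point: the LOCF text does not say that the carried score must be post-baseline. The only earlier mRS is the pre-ICH score, which eligibility limits to 0–1, so carrying it forward would count as a good outcome. This could matter only for a subject lost before the day-7 or discharge assessment.

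**Working it through.** **The plan's own figure (section 8.4).** With 0.28 in both arms, margin 0.12, one-sided alpha 0.10 and power 0.80: n per arm = 2 × 0.28 × 0.72 × (1.2816 + 0.8416)² / 0.12² = 126.2, rounded up to 127, so 254 in total. Then 254 × 1.11 × 1.04 = 293.2, rounded up to 294. Both figures reproduce, and the concern does not touch them.

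**Scale.** 294 / 1.04 = 282.7 treated subjects, about 141 per arm. At 5% missing, about 14 outcomes are imputed, 7 per arm.

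**Assumptions (not in the protocol).**

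- The chance of day-90 mRS 0–2 is 0.75 if the last interim score was 0–2, and 0.05 if not.
- True rates are 0.40 v 0.28 (at the margin) or 0.28 v 0.28 (no effect).
- The interim-good share is q = (p − 0.05)/0.70, which is 0.500 for p = 0.40 and 0.329 for p = 0.28.
- Loss is 3:1 by interim status, in opposite directions by arm.
- ρ is the correlation between baseline and latent interim status, taken as 0, 0.5 or 0.7.

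**Closed form at ρ = 0, 5% missing, 0.40 v 0.28.** Interim-good subjects are lost more often on DFO, interim-poor more often on placebo.

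- DFO loss rates: 0.075 (good) and 0.025 (poor). Observed rate = (0.5 × 0.925 × 0.75 + 0.5 × 0.975 × 0.05)/0.95 = 0.3908.
- Placebo loss rates: 0.0213 (good) and 0.0640 (poor). Observed rate = (0.3286 × 0.9787 × 0.75 + 0.6714 × 0.9360 × 0.05)/0.95 = 0.2869.
- Difference = 0.1039 against a true 0.12. With 141 × 0.95 observed per arm, SE = 0.0575.
- P(declare futility) = Φ[(0.12 − 0.1039)/0.0575 − 1.2816] = 0.159 against a nominal 0.10.
- LOCF in the same case counts the lost interim-good subjects as good: DFO 0.4088, placebo 0.2796, difference 0.129, false futility 0.07.

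At 3% missing the same steps give a difference of 0.1105 and false futility of 0.132. At 10%, the crude Phase I withdrawal rate, they give 0.086 and 0.24.

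**Closed form at ρ = 0, loss pattern reversed, 0.28 v 0.28, 5% missing.** DFO is observed at 0.2869 and placebo at 0.2702. The difference is 0.0167 with SE 0.0548, so the power to declare futility is Φ[(0.12 − 0.0167)/0.0548 − 1.2816] = 0.73.

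**Simulation with baseline information.** 8,000 trials, 20 imputations, Rubin's rules, and an adjusted identity-link linear model with robust SE standing in for the binomial model; Monte Carlo SE 0.003–0.005. Each cell gives baseline-only v interim score added:

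| Missing | ρ | False futility, 0.40 v 0.28 | Power, 0.28 v 0.28, loss reversed |
|---|---|---|---|
| 5% | 0 | 0.156 v 0.099 | 0.734 v 0.825 |
| 5% | 0.5 | 0.147 v 0.103 | 0.759 v 0.842 |
| 5% | 0.7 | 0.139 v 0.100 | 0.801 v 0.864 |
| 3% | 0 | 0.140 v 0.107 | 0.785 v 0.836 |
| 3% | 0.5 | 0.128 v 0.097 | 0.805 v 0.848 |
| 3% | 0.7 | 0.116 v 0.095 | 0.833 v 0.866 |

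In large samples the bias of the baseline-only model at 5% is −0.0161, −0.0136 and −0.0110 for ρ = 0, 0.5 and 0.7. At 3% it is −0.0095, −0.0080 and −0.0065.

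**Random loss, 5%.** False futility is 0.10 under either model. Adding interim scores gains at most about one point of power (0.814 to 0.823 at ρ = 0; 0.853 to 0.860 at ρ = 0.7).

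**A second simulation with different assumptions.** Baseline explains 40% of latent outcome variance, interim status has residual correlation 0.6 to 0.85 with day 90, and the loss pattern is the reversed one. At 5% missing, the baseline-only model shifts the difference by +0.012 to +0.018. Power at no effect falls from about 0.83 to 0.73–0.76, and false futility falls to 0.06–0.07. With interim status added, the remaining shift is at most 0.0005.

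**The case against.** Multiple imputation given arm and baseline is a legitimate missing-at-random method, and section 8.5 contains no contradiction. The harmful pattern requires loss to run in opposite directions in the two arms of a double-blind trial, and the protocol gives no reason to expect that. Telephone and proxy mRS, and follow-up after stopping study drug, keep loss low. The worst bias in the main setting, 0.0161, is about 2.3 outcomes in an arm of 141, or 0.29 of a standard error. The ρ = 0 case is close to an upper bound, because ICH score, ICH volume and NIHSS do predict outcome. The sign of the bias follows the assumed pattern. LOCF is already planned and would show a visible gap. Section 3.3 also says the design worries less about letting an ineffective treatment through. Finally, a statistical analysis plan, which was not available here, could name further predictors.

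Most of this stands, and it is why the point is a suggestion. Three things limit it:

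- The *i.e.* clause fixes the classes of data used, so an analysis plan that added follow-up scores would depart from the protocol.
- LOCF reveals a problem without changing the primary test, and it is not correct either: in the 5% example the truth is 0.120, the primary analysis gives 0.104 and LOCF 0.129.
- Telephone follow-up does not help after withdrawal of consent, which section 8.4 counts as part of its 5%.

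**Conclusion.** The concern holds as a low-cost improvement. The primary imputation is defined without the follow-up mRS scores that the trial collects.

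Under random loss, or loss alike in both arms, the effect is negligible. Under the assumed 3:1 arm-opposite loss with 3–5% missing, false futility is about 0.12–0.16 instead of 0.10. With the pattern reversed and no true effect, power to declare futility is 0.73–0.83 instead of 0.83–0.87. Where baseline is moderately predictive (ρ 0.5–0.7), false futility is 0.12–0.15.

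These figures rest on assumed loss patterns and an assumed link between interim and day-90 status. The near-complete correction arises because loss was made to depend on the interim score. If loss depends on the day-90 outcome itself, adding interim scores removes only part of the bias: 32–65% in simulation at ρ = 0, and 16% when the early score is weak. No bias is demonstrated for this trial.

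**What to change.** In section 8.5, state that the imputation model includes the available post-baseline mRS scores (day 7 or discharge, day 30, day 60, and day 180 where known) together with treatment arm and the randomization covariates. State that LOCF carries forward post-baseline scores only, and keep it as the planned sensitivity analysis. Section 8.3 can stay as it is for never-treated subjects. Section 8.4 and the sample size need no change.

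The cost is one or two sentences and minor programming, with no added patients or visits. Interim scores that are themselves missing must be imputed in the same step. There is little gain for subjects lost very early, and day-180 mRS will not exist after withdrawal of consent.

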PHYSIOLOGICAL DATA: Laboratory data - There were no differences in routine laboratory values and in the incidence of abnormalities and change from baseline in EKG parameters. Overall, daily DFO infusions at a rate of 7.5 mg/kg/hour up to 62 mg/kg/day (up to a maximum of 6000 mg/day) were well tolerated without significant alterations of hemoglobin or hematocrit, hematological parameters, and renal or hepatic functions. Treatment with DFO for 3 consecutive days at all 5 dose-tiers did not result in iron deficiency. Overall, the median values of the change in iron parameters from baseline to after the 3rd DFO infusion were as follows: serum iron (3.5 ug/dl; 95% CI -23, 45); transferrin (-18 ng/ml; 95% CI -43, 5); total iron binding capacity (8.5 ug/dl; 95% CI -47, 30); and ferritin (32.5 ng/ml; 95% CI 6, 74). We found no relationship between DFO dose and changes in serum iron studies. Vital signs (heart rate, respiratory rate, oxygen saturation, and temperature) - Overall, DFO administration did not result in important alterations in these variables. Blood pressure: DFO had a moderate BP-lowering effect. Overall, the median mean BP at baseline was 95.8 mmHg (95% CI 84, 100.3) vs. 93.2 mmHg (95% CI 87.6, 98) during the infusions. A total of 8 patients (40%) experienced a maximal drop in mean BP >20% (median 0.29; 95%CI 0.27, 0.39) at some point during the infusions compared to baseline values. One subject required vasopressors; his hypotension was thought to be related to intubation and anesthesia. None of the remaining 7 subjects required any medical treatment.

RADIOLOGICAL DATA: We found no radiological evidence to suggest that treatment with DFO exacerbates the natural enlargement of ICH or PHE over 72h after treatment. The overall median change in relative PHE volume from screening to post-3rd DFO infusion was 0.48 (95% CI 0.10, 0.76) and from screening to day-7 or discharge (whichever

occurred first) was 0.87 (95% CI 0.51, 1.28). These exploratory results contrast with previous studies of the natural history of relative PHE evolution [Mehdiratta 2008; Gebel 2002], which showed that the relative PHE volume almost doubles by 72h.

FUNCTIONAL OUTCOME DATA: Two subjects withdrew consent, one after the 7-day visit (mRS =5), and one after the 30-day visit (mRS =1). Among the remaining 18 subjects, 9 subjects (50%) had mRS scores of 0-2; 2 (11%) had a score of 3; and 7 (39%) had scores of 4-6. The 90-day mortality rate was 15%.

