4.1 Inclusion Criteria

- 1) Age ≥ 18 and ≤ 80 years
- 2) The diagnosis of ICH is confirmed by brain CT scan
- 3) NIHSS score ≥ 6 and GCS >6 upon presentation.
- 4) The first dose of the study drug is expected to be administered within 24h of ICH symptom onset (as described above).
- 5) Functional independence prior to ICH, defined as pre-ICH mRS ≤ 1 .
- 6) Signed and dated informed consent is obtained.

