4.3.2 SCREENING EVALUATIONS

The following clinical, laboratory, and radiological assessments will be carried out upon screening of potential study subjects: 1) Demographic data; 2) Medical history; 3) Review of medications; 4) General physical examination and vital signs; 5) Neurological examination, including visual auditory assessment, NIHSS, and GCS; 6) Review of head CT scans and chest x-rays; 7) Review of all inclusion/exclusion criteria; 8) Determination of ICH score and pre-ICH mRS score; 9) Laboratory tests (hematology, serum chemistries, serum albumin, coagulation parameters, renal and hepatic function tests and urine analysis).

A baseline pre-treatment plain (non-enhanced) brain CT confirming the presence of ICH is required to establish the diagnosis of ICH. The head CT should be reviewed by a Radiologist or a stroke-trained Neurologist experienced in the interpretation of CT scans. The need for additional diagnostic tests, such as CTA, conventional angiogram, or MRI/MRA to rule out secondary causes of ICH in suspected cases should be based on the judgment of the investigators according to the standards of clinical practice at each participating institution and the guidelines from the Stroke Council of the American Heart Association [Morgenstern, 2010; please refer to appendix II].

A baseline chest x-ray is required before enrollment to exclude the presence of bilateral pulmonary infiltrates or pulmonary edema.

A negative serum pregnancy test is required for all women of childbearing potential prior to enrollment into the study.

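### The LOCF rule in section 8.5 is not limited to post-stroke mRS scores, and it is a weak check on a futility conclusion

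*Protocol*

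**What the plan says.** Section 8.5 of the protocol sets the primary method: "Missing primary outcome data will be imputed via standard multiple imputation (MI) methods", through a "logistic regression model predicting outcome based on pertinent baseline and treatment data". The check on it follows: "As a sensitivity assessment, we will use the Last Observation Carried Forward (LOCF) approach", under which "the last available score will be carried forward for missing day 90 assessments". The section expects the two methods to lead to similar conclusions if the treatment effect is robust, above all when less than 5% of outcomes are missing.

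The schedule in section 6.2 puts mRS at screening, at day 7 or discharge (whichever is first), and at days 30, 60, 90 and 180. Section 4.3.2 shows what the screening entry is: "Determination of ICH score and pre-ICH mRS score". Section 4.1 admits only subjects with "Functional independence prior to ICH, defined as pre-ICH mRS" of at most 1. Section 8.2.1 defines a good outcome as mRS 0-2 at 90 days and declares futility when the one-sided 90% upper bound on the risk difference lies below 0.12.

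Section 8.3 puts in the modified ITT sample everyone whose infusion began. Only the per-protocol sample requires a post-treatment assessment. Under section 7.4, subjects who stop study drug are followed to day 180 unless they withdraw consent.

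**The concern.** Taken together, these sections leave a gap in the carry-forward rule. A subject whose infusion starts and who withdraws consent in hospital, before the day-7 or discharge mRS, belongs to the modified ITT sample and has one mRS on file: the pre-stroke one. The literal rule scores that subject 0 or 1, a good outcome, whatever the stroke did.

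For later dropouts, the carried score dates from a period when patients are still recovering. Section 3.3 itself gives the longer recovery of ICH patients as a reason for adding six-month follow-up.

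The design makes this more than a tidiness issue. The null hypothesis is a benefit of at least 12 points, so anything that dilutes a real difference pushes towards declaring futility. The useful question for a sensitivity analysis is how favourable the missing DFO outcomes would have to be before futility no longer holds. LOCF does not ask it. For treated subjects with a missing day-90 mRS, it is the only alternative to multiple imputation that the protocol names.

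**Working it through.** **Inputs.** From sections 8.2.1 and 8.4: control rate 28%, margin 0.12, one-sided alpha 0.10 (z = 1.2816), power 80% (z = 0.8416), drop-out 5%, inflation factors 1.11 and 1.04. The missing-data splits between arms and the good-outcome rates that LOCF assigns are assumptions, since the protocol gives none.

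**1. The protocol's own sample size.**
- n per arm = (1.2816 + 0.8416)² × 2 × 0.28 × 0.72 / 0.12² = 4.508 × 28 = 126.2, so 127 per arm and 254 in total, as stated.
- 254 × 1.11 × 1.04 = 293.2, so 294, as stated.
- Treated subjects: 294 / 1.04 is about 282, or 141 per arm. Five per cent of 141 is about 7.

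**2. Largest observed difference that still gives futility** (both arms near 28%, unadjusted normal approximation): 0.12 − 1.2816 × SE.
- 141 per arm: SE = √(0.4032/141) = 0.0535; limit 0.051.
- 127 per arm: SE = √(0.4032/127) = 0.0563; limit 0.048.

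**3. LOCF with balanced 5% loss, truth 40% v 28%, 141 per arm.** Arm rate = 0.95 × true rate + 0.05 × q, where q is the good-outcome rate that LOCF assigns to dropouts.
- All carried as not good (q = 0): 38.0% − 26.6% = 11.4 points.
- All carried as good, the pre-ICH case (q = 1): 43.0% − 31.6% = 11.4 points.
- In both cases P(difference + 1.2816 × SE < 0.12) is about 0.12, against 0.10 with complete data.
- If q is half the day-90 rate in each arm (20% and 14%), the difference is 11.7 points and the probability 0.11.

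So the shrinkage is at most 0.6 points, provided q is no lower on DFO than on placebo.

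**4. LOCF with imbalanced loss** (assumed splits, truth 40% v 28%):

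| Loss DFO / placebo | Carried as | Difference (points) | P(false futility) |
|---|---|---|---|
| 7.5% / 2.5% | good | 14.7 | 0.04 |
| 7.5% / 2.5% | not good | 9.7 | 0.19 |
| 2.5% / 7.5% | good | 8.1 | 0.27 |
| 2.5% / 7.5% | not good | 13.1 | 0.07 |

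The direction depends on which arm loses subjects and when they leave.

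**5. Extreme bound, 5% missing per arm.** Score every missing DFO subject good and every missing placebo subject not good.
- Both arms truly 28%: shift = 0.05 × 0.72 + 0.05 × 0.28 = +5.0 points. The probability of declaring futility falls from 0.83 to 0.51. The reverse scoring gives −5.0 points and 0.97.
- Truth 40% v 28%: shifts of +4.4 or −5.6 points. False futility runs from 0.02 to 0.39, against 0.10.
- An observed difference of zero becomes 31.6% v 26.6%. Its upper bound is 0.05 + 1.2816 × 0.0540 = 0.119 with 141 per arm, and 0.05 + 1.2816 × 0.0569 = 0.123 with 127. These lie on either side of 0.12.

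**The case against.** The other side has several good points.

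- **The protocol never says that the pre-ICH score will be carried.** A reader might infer that it does. The text only fails to exclude it, and the score is collected to establish eligibility. Which visits feed LOCF may be settled in the SAP, which is not at hand. This stands: the fault is an open rule, not a stated error.
- **Few subjects are affected.** Leaving hospital early triggers the first post-stroke mRS, stopping drug does not end follow-up, and a death has an mRS of its own and is not missing. Phase I (section 2.2.2, functional outcome data) reported two withdrawals among 20 subjects, "one after the 7-day visit (mRS =5), and one after the 30-day visit (mRS =1"), and none before day 7. With 0 of 20, the 95% upper limit is 1 − 0.05^(1/20) = 14%, so the data are thin, but a small group is the likely case.
- **LOCF need not pull the result down.** In Phase I it gives 10/20 good outcomes, the same 50% as the 9/18 completers. Someone lost after the day-60 call carries a two-month score. A reader might infer that LOCF always favours futility; step 4 shows that it does not.
- **The 12% is not the trial's error rate.** A reader might infer that the futility test is inflated. The primary analysis uses multiple imputation, and the figure applies only to a decision taken on LOCF.
- **Section 8.5 does not claim that agreement proves robustness.** It says that robustness should lead to agreement. It would also be too strong to say that LOCF cannot test a futility call: it does test it, weakly.
- **The 5-point bound belongs to 5% missingness, not to LOCF.** That is correct. It shows what the named check leaves unexamined.

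The absence of a tipping-point analysis from a protocol is not in itself a fault. What remains open to criticism is the text that section 8.5 does fix: the method and its carry-forward rule.

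**Conclusion.** The point holds in a limited form. The stated LOCF rule admits the pre-ICH mRS and so can record a good outcome for a treated subject with no post-stroke score. Under balanced 5% loss its effect is modest: about 0.6 points, and about 12% rather than 10% false futility for a decision based on LOCF. Under the assumed imbalances that figure runs from 4% to 27%, so the error can go either way.

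LOCF is therefore a weak check on a futility call. The extreme 5-point shift at 5% missing is about as large as the biggest observed difference that still gives futility (4.8 to 5.1 points), so a futility call near an observed difference of zero could sit at the edge in the worst case.

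These figures rest on the protocol's 28% control rate and 5% loss, an unadjusted normal approximation, and assumed drop-out splits and carried scores. They do not call the primary analysis into question. The change is worth making because it costs little in a trial meant to decide whether to go on to Phase III.

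**What to change.** In section 8.5:

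1. State that any LOCF uses only mRS scores obtained after the stroke (day 7 or discharge onwards), and that the pre-ICH score is never carried. Treated subjects with no post-stroke score then need a stated route, for example the multiple imputation.
2. Replace or supplement LOCF with a tipping-point analysis on the multiple imputation. Raise the imputed probability of a good outcome on DFO and lower it on placebo in steps, and report where the one-sided 90% upper bound reaches 0.12.

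The cost is a sentence or two of text and a small amount of extra analysis, with no new data and no change to sample size or visits.
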